8.2 Special Considerations

The 25-hydroxyvitamin D levels which are checked in the study are not revealed to the patient and doctor unless they specifically request that information, or if any of the calcium or Vitamin D levels exceed the pre-specified thresholds laid out in [Section 8.1](#). However, if the physician or patient wishes to know her vitamin D level, they may obtain this information from the study coordinator. For those who are on the standard dose vitamin D arm and have vitamin D <20 ng/mL, the physician may choose to replace vitamin D levels with 4000 IU of vitamin D3 daily, beginning at any point *after* 12 weeks of study enrollment. Vitamin D level will be checked every 4 weeks until it is ≥30 mg/mL. At that point, the patient will resume Caltrate-D once daily for the remainder of the study period.

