1.5 Vitamin D Background

While the relationship of Vitamin D to breast cancer risk and recurrence clearly needs further study, Vitamin D deficiency is well known to cause a wide array of musculoskeletal issues, including diffuse skeletal pain and non-inflammatory arthritis. For example, among 1993 post-menopausal women from the Womens Health Initiative, low vitamin D levels were correlated with increased joint pain (34). Furthermore, in non-cancer patients, these symptoms have resolved and/or improved with single high dose vitamin D3 at 150,000 IU orally (35) (36) (37).

Optimal levels of Vitamin D are not completely agreed upon, as deficiency is usually defined as a serum 25-hydroxy vitamin D level <20 ng/mL, as supported by the Institute of Medicine (38). However, there is evidence to state that proximal muscle strength improves as vitamin D levels increase to >40 ng/mL (39). Vitamin D insufficiency and deficiency are quite common among post-menopausal breast cancer patients, ranging from 75-90% (33) in some reports, though vitamin D levels are known to vary based on geographic location. However, the tie between post-menopausal women on AI therapy and low vitamin D levels is logical because estrogen and vitamin D are closely linked. Estrogen increases activity of 1 alpha hydroxylase, which catalyzes conversion 25(OH)D to its active form, 1,25(OH)2D. Estrogen also increases the activation of the Vitamin D receptor.

Therefore, it is reasonable to suppose that a low estrogen state, as is seen in women on AI therapy, could potentially decrease the amount of active Vitamin D available, and studies have corroborated this. One retrospective analysis of the International Breast Cancer Intervention (IBIS-II) trial found that among 416 post-menopausal women who were at high risk of breast cancer, only 13% had adequate vitamin D levels (≥ 30 ng/mL), 41% had inadequate levels (20-30 ng/mL), and 46% were deficient or severely deficient (< 20 ng/mL) (40). Similarly, in the AZURE trial, only 10% of women had adequate Vitamin D levels of > 30 ng/mL, even when seasonal variation was properly accounted for (33). Clearly, Vitamin D deficiency is quite common among women internationally, and it merits further study.

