3. STUDY DESIGN/SUMMARY

This is a randomized, multi-center, controlled, phase II study comparing high dose vitamin D vs. standard dose vitamin D for post-menopausal breast cancer patients who are beginning adjuvant aromatase inhibitor therapy. The study is intended to be conducted in up to 5 centers within the U.S.A which are routinely engaged in the administration of aromatase inhibitor therapy for the study specified population. All patients who are starting an AI in the adjuvant setting are eligible to participate in the study.

In order to preserve power and compensate for the interim futility analysis which tends to reduce power, the sample size of the study is increased from 88 per group to 93 per group, which is 186 total if considering a 5% drop out rate. A total of 186 patients at up to 5 centers will be randomized 1:1 to receive either 50,000 International Units (IU) oral vitamin D per week for 12 weeks followed by 2000 IU daily for 40 weeks, or 800 IU Vitamin D daily for 52 weeks. All women on both arms of the trial will also take calcium carbonate 600 mg daily.

The primary endpoint for this study is development of AIA in each arm after 12 weeks of AI therapy, as determined by patient questionnaires. Secondary endpoints include compliance with AI therapy, as well as correlation of low baseline vitamin D levels with development of AIA. Grip strength is an exploratory endpoint.

[figure not shown]
Throughout the 52 week study period, participating women will complete the questionnaire and grip strength measurement a total of three times in order to assess their arthralgia while on AI therapy. Compliance with aromatase inhibitor (AI) therapy will also be assessed throughout the

Vitamin D for AIA

study to determine if AI compliance is improved in women who are receiving Vitamin D. Additionally, women will also have periodic assessments of serum 25-hydroxyvitamin D to assess whether vitamin D levels correlate with AIA, and to ensure that calcium and 25(OH) D levels are within healthy ranges.

SCHEMA

High Dose vs. Standard Dose Vitamin D for Aromatase Inhibitor-Induced Arthralgia

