5. REGISTRATION PROCEDURES

5.1 Guidelines

Patients should be registered in the electronic database as soon as the patient has signed the informed consent. Following registration, the patient's enrollment status in the electronic database will be listed as pending. Prior to enrollment in the electronic database, the eligibility worksheet must be reviewed and signed by the study coordinator and a Breast Center physician investigator, in accordance with Lester & Sue Smith Breast Center clinical research standard operating procedures. Eligibility data will then be entered in the electronic database and the subject will be randomized.

Study treatment may begin only after eligibility has been confirmed by both a study coordinator and a Breast Center physician. Once eligibility has been reviewed, it is recommended that treatment begin within a timely manner. Although there is no protocol-required timeframe, every effort will be made to ensure that study treatment begins within 7-14 days of subject enrollment.

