6.1 Screening and Baseline assessments

A signed, written informed consent must be obtained before any study-specific assessments are initiated. Results from assessments performed prior to written consent as part of a patient's routine diagnostic workup may be used for screening purposes. The following assessments will be obtained at screening, within 28 days prior to beginning study medication:

- Subject demographic information, to include age, ethnicity, and race
- Medical history, including past and current conditions, and past surgical history
- Whether patient has used Hormone Replacement Therapy (HRT), for how many years, and how long ago she stopped.
- Use of chemotherapy, including taxanes or not including taxanes
- Measurement of body weight, height, and Body Mass Index
- Completion of Health Assessment Questionnaire (HAQ-II)

- Grip strength measurement
- Laboratory assessments to include:
 - Calcium level
 - Albumin level
 - Vitamin D level -- serum 25(OH)D
 - FSH, LH, and estradiol levels must be obtained if required as detailed above in 4.1.4 to determine menopausal status. Menopausal status should be interpreted by the treating physician and approved by study chair based on the cutoff values provided by the reporting laboratory.
- Review of all medications taken within 28 days of planned treatment start date
- Study coordinator will educate the patient about the importance of compliance with Aromatase Inhibitor therapy.
- If a Bone Mineral density test has not been completed within 3 months of starting AI therapy, a Bone Mineral Density test must be ordered as a screening assessment, and the test must be completed within 28 days of starting Aromatase Inhibitor therapy

If the above studies are within acceptable parameters as defined by the eligibility criteria, the patient will be randomized to begin either high dose Vitamin D or standard dose Vitamin D, as described in [Section 7](#).

6.2 Follow-up at Week 4

The following assessments should be performed at 4 weeks (28 days) from the start of study medication. To allow for weekends, holidays, etc., study procedures may be completed within a window of +/- 5 business days.

- Laboratory assessments to include a calcium level, 25-hydroxyvitamin D level, and albumin.

6.3 Follow-up at Week 12

- Measurement of body weight and BMI
- Laboratory assessments to include a calcium level, 25-hydroxyvitamin D level, and albumin.
- Patient is to complete the Health Assessment Questionnaire (HAQ-II)

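### Section 8.2 times standard-arm vitamin D replacement from enrolment, a clock not shared with the Week-12 HAQ-II, and states its end level in an unreachable unit

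*Combined protocol and SAP*

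**What the plan says.** Section 8.2 sets an optional replacement rule for the standard-dose arm. For women who "have vitamin D <20 ng/mL, the physician may choose to replace vitamin D levels with 4000 IU of vitamin D3 daily", replacement may begin at any point after "12 weeks of study enrollment", with the word *after* emphasised. It continues as follows: "Vitamin D level will be checked every 4 weeks until it is ≥30 mg/mL". Only then does the woman go back to one Caltrate-D daily.

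The other clocks in the protocol are these:

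- Section 5.1, on the interval from enrolment to treatment: "every effort will be made to ensure that study treatment begins within 7-14 days of subject enrollment". The same sentence says that no timeframe is required.
- Section 6.2, on the Week 4 visit: "The following assessments should be performed at 4 weeks (28 days) from the start of study medication".
- Section 6.3, on the Week 12 visit where the primary HAQ-II is completed, gives neither an origin nor a window.
- Section 3: "The primary endpoint for this study is development of AIA in each arm after 12 weeks of AI therapy".

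Section 13.4 tests the primary objective on AIA at Week 12 and also reports Week 52. Section 8.1 gives every 25(OH)D limit in ng/mL.

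**The concern.** The emphasis on *after* suggests that replacement was meant to wait until the primary assessment was done, although the protocol does not state the reason. Counting from enrolment does not guarantee that order. Whenever the clock for Week 12 starts later than enrolment, the rule opens before the primary HAQ-II is due, and a control woman may receive more vitamin D than assigned before her primary outcome is recorded. If vitamin D does reduce AIA, such exposure would pull the control arm towards the high-dose arm.

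The second problem is separate. The level that ends replacement is an operative threshold, and in the unit written it cannot be met. Women on replacement would then have no level-based return to assigned treatment, which bears on the Week 52 AIA data.

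**Working it through.** The plan gives no figure for the gap, so there is nothing to reproduce. The check is date arithmetic and a unit conversion.

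**Inputs**

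- The rule opens after 12 × 7 = 84 days from enrolment (Section 8.2).
- L is the number of days from enrolment to first study medication. The Section 5.1 target is a ceiling, so L runs from 0 to 14 at target. No maximum is required.
- A is the number of days from enrolment to AI start. The documents do not fix it. Section 4.1.5 requires that the woman is beginning AI therapy with no use in the previous 6 weeks.
- Daily doses are 4000 IU on replacement (Section 8.2, read as taking the place of Caltrate-D, since Caltrate-D is later resumed) and 800 IU as assigned (Section 6.9.3).

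**Step 1: Week 12 counted from study medication (assumption, extending Section 6.2).** The visit falls on enrolment day L + 84, so the gap is (L + 84) − 84 = L.

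| L (days) | Week-12 visit, enrolment day | Gap (days) | IU at 4000/day | IU at 800/day |
|---|---|---|---|---|
| 0 | 84 | 0 | 0 | 0 |
| 7 | 91 | 7 | 28,000 | 5,600 |
| 14 | 98 | 14 | 56,000 | 11,200 |
| 28 (assumed; not forbidden by 5.1) | 112 | 28 | 112,000 | 22,400 |

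**Step 2: Week 12 counted from AI start (Section 3).** The gap is A. It is zero if AI therapy starts on the day of enrolment, positive if later, and absent if earlier.

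**Step 3: visit window.** For Week 4, "study procedures may be completed within a window of +/- 5 business days", about 7 calendar days either way. If that also applied at Week 12 (an assumption), the gap in Step 1 would run from L − 7 to L + 7: 0 to 14 days for L = 7, and 7 to 21 days for L = 14.

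**Step 4: who can be exposed.** All of these must hold: standard arm; level below 20 ng/mL; the level is requested, because Section 8.2 otherwise keeps it from patient and doctor unless a Section 8.1 threshold is exceeded; the physician chooses to replace; and replacement starts inside the gap. The scheduled levels before Week 12 are baseline and Week 4 (Appendix B). The next is drawn at the Week 12 visit itself. So exposure before the primary HAQ-II would normally rest on the baseline or Week 4 result. The documents give no count of such women.

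**Step 5: end level.** 1 mg/mL = 1,000,000 ng/mL, so 30 mg/mL = 30,000,000 ng/mL. Section 8.1 takes any patient off study medication above 120 ng/mL, and 30,000,000 / 120 = 250,000. The end condition is 250,000 times the stopping level and cannot be met. The same number in ng/mL would lie above the 20 ng/mL trigger and below the 70, 90 and 120 ng/mL levels of Section 8.1, and Section 1.5 uses 30 ng/mL as the bound for an adequate level.

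**Step 6: literal duration.** With no reachable end level, replacement begun at about Week 12 could run to the end of treatment at Week 52 (Section 6.5), that is 52 − 12 = 40 weeks, subject to the Section 8.1 limits. Over those weeks the high-dose arm takes 2000 IU daily (Section 6.9.2), so for these women the dose contrast would be reversed.

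**The case against.** The strongest reply is that the gap rests on an origin the protocol never states for Week 12. A reader might infer that the Week-12 HAQ-II is counted from study medication. The wording says so for Week 4 only, and Section 3 points to AI therapy instead. There is indirect support: Section 6.5 ties Week 52 to completion of study therapy, and Section 7.2 supplies the 2000 IU capsules for weeks 13-52, after the 12-week high-dose phase. That makes the study-medication clock likely but does not settle it. On the AI clock, with AI therapy begun on or before enrolment, the gap disappears. This objection stands, and it turns the point into one about an undefined origin.

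Three other strong readings are also unsupported:

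- *The gap is at least 7 days.* Section 5.1 states a target to start within 7-14 days. A same-day start satisfies it, so the lower end is 0 days and 0 IU.
- *Replacement never ends.* Only the level criterion is unreachable. Week 52 and the Section 8.1 limits still apply.
- *The primary comparison is biased.* The documents show only that it could be. The conditions in Step 4 must all hold, and nothing says how often they do.

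It is also fair to say that mg/mL is probably a one-letter slip that most sites would read through, given the ng/mL in the same paragraph. That lowers the practical risk. It does not make the text right, since this is a threshold that up to five sites must apply.

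**Conclusion.** The point holds as a minor inconsistency in a stated rule. Three possible clocks (enrolment, study medication, AI start) bear on 12 weeks, and the documents do not reconcile them. On the study-medication clock, replacement can open 0-14 days before the primary HAQ-II at the target lag, allowing 0-56,000 IU against 0-11,200 IU as assigned, and by longer if treatment starts later than the target. The direction of any effect is towards a smaller difference between arms. Its size cannot be estimated from the documents and is probably small.

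The end level in mg/mL is wrong as written whichever clock applies. Read literally, it leaves some control women on replacement for up to about 40 weeks, within the Section 8.1 limits, and so could affect the Week 52 AIA comparison. It does not bear on the Week 12 test except through the gap above.

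**What to change.** Reconcile Sections 3, 5.1, 6.2, 6.3 and 8.2 so that 12 weeks has one stated origin, used for both the replacement rule and the primary HAQ-II. Reconcile the unit of the end level in Section 8.2 with the unit used in the rest of Sections 8.1 and 8.2. Which origin and which replacement criteria are clinically right is for the investigators; nothing here proposes a dose or a rule.

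The cost is a few phrases in a protocol amendment. Sample size, test and analysis are unchanged.

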9. ADVERSE EVENTS & SAFETY MONITORING

9.1 General

Adverse event collection and reporting is a routine part of every clinical trial. This study will use the descriptions and grading scales found in the NCI Common Terminology Criteria for Adverse Events version 4.0 (CTCAE v4.0) that is available at <http://ctep.cancer.gov/reporting//ctc.html>.

Information on certain adverse events, whether reported by the participant, directly observed, or detected by physical examination, laboratory test or other means, will be collected, recorded, followed and reported as described in the following sections.

Adverse events experienced by participants will be collected and reported from initiation of study medication, throughout the study, and within 30 days of the last dose of study medication. Participants who experience an ongoing adverse event related to a study procedure and/or study medication beyond 30 days will continue to be contacted by a member of the study team until the event is resolved, stabilized, or determined to be irreversible by the participating investigator.

Participants should be instructed to report any serious post-study event(s) that might reasonably be related to participation in this study. The investigator should notify the IRB and any other applicable regulatory agency of any unanticipated death or adverse event occurring after a participant has discontinued or terminated study participation that may reasonably be related to the study.

9.2 Definitions

9.2.1 Adverse Event (AE)

An adverse event is any undesirable sign, symptom or medical condition or experience that develops or worsens in severity after starting the first dose of study treatment or any procedure specified in the protocol, even if the event is not considered to be related to the study.

Abnormal laboratory values or diagnostic test results constitute adverse events only if they induce clinical signs or symptoms or require treatment or further diagnostic tests.

9.2.2 Serious adverse event (SAE)

A serious adverse event is an undesirable sign, symptom, or medical condition which:

- is fatal or life-threatening;

- requires or prolongs inpatient hospitalization;
- results in persistent or significant disability/incapacity;
- constitutes a congenital anomaly or birth defect; or
- jeopardizes the participant and requires medical or surgical intervention to prevent one of the outcomes listed above.
- Any other event, which, in the opinion of the investigator, could be considered serious.

Events **not** considered to be serious adverse events are hospitalizations for:

- routine treatment or monitoring of the studied indication, not associated with any deterioration in condition, or for elective procedures
- elective or pre-planned treatment for a pre-existing condition that did not worsen
- emergency outpatient treatment for an event not fulfilling the serious criteria outlined above and not resulting in inpatient admission
- respite care

9.2.3 Expectedness

- Expected: Expected adverse events are those that have been previously identified as resulting from administration of the agent. For the purposes of this study, an adverse event is considered expected when it appears in the current adverse event list, the Investigator's Brochure, the package insert or is included in the informed consent document as a potential risk.
- Unexpected: An adverse event is considered unexpected when it varies in nature, intensity or frequency from information provided in the current adverse event list, the Investigator's Brochure, the package insert or when it is not included in the informed consent document as a potential risk

9.2.4 Attribution

The investigator will determine the relationship of each adverse event, if any, to investigational treatment or study procedure. Causality should be assessed using the following categories: Unrelated, Unlikely, Possible, Probable, or Definite.

The degree of certainty with which an adverse experience is attributed to drug treatment (or alternative causes, e.g. natural history of the underlying diseases, concomitant therapy, etc.) will be determined by how well the experience can be understood in terms of the following:

- Known pharmacology of the drug
- Reaction of similar nature being previously observed with this drug or class of drug
- The event having often been reported in literature for similar drugs as drug related (e.g. skin rashes, blood dyscrasias)
- The event being related by time to drug administration terminating with drug withdrawal (dechallenge) or reproduced on rechallenge.

The investigator may change his/her assessment of causality in light of follow-up information. All adverse events will be recorded, regardless of whether the event is thought to be related to investigational treatment. Attribution will be assigned as follows:

- Definite – The AE is clearly related to the study treatment.
- Probable – The AE is likely related to the study treatment.
- Possible – The AE may be related to the study treatment.
- Unlikely - The AE is doubtfully related to the study treatment.
- Unrelated - The AE is clearly NOT related to the study treatment.

9.3 Anticipated Toxicities

If Vitamin D levels are allowed to become too high, hypercalcemia is the most common side effect. Symptoms may include anorexia, nausea, vomiting, abdominal pain, confusion, lethargy, constipation, muscle weakness, weight loss, polyuria, kidney stones, and heart arrhythmias.

9.4 Toxicity Management

Calcium and 25-hydroxyvitamin D levels will be followed closely while the patients are on study to avoid hypervitaminosis D. Levels of 25-hydroxyvitamin D and calcium will be monitored and managed as outlined in [Section 8.1](#). For corrected calcium level greater than 11 g/dL, management will be according to standard of care and the judgment of the treating physician. It is recommended that the patient be hydrated with one liter of IV normal saline, and given one dose of pamidronate at 90 mg IV, if renal function is within normal limits. The use of calcitonin will be at the treating

physician's discretion. The patient will be followed closely and treated until the calcium level normalizes. The patient will not be re-challenged with the study medication in this case.

If the patient develops calcium kidney stones, she will also be taken off the study. She will be referred to her primary care physician and/or urology for further management of the kidney stones.

9.5 Adverse event follow-up

Investigators should follow-up subjects with adverse events until the event has subsided (disappeared) or until the condition has stabilized. Subjects will be followed for adverse events and serious adverse events for 30-days from the last dose of study drug.

During the 30-day follow-up period, new onset, non-serious adverse events should only be recorded if, in the opinion of the investigator, there is a reasonable possibility the event is attributable to the investigational product. All serious adverse events occurring within the 30-day follow-up period must be reported, regardless of suspected causality.

